4.3 Verification of Statistical Assumptions

4.3.1 For Repeated Measures ANOVA:

Assumption of Normality:

- **Primary method:** Shapiro-Wilk test ($n \leq 50$ appropriate for $n=24$).
- **Complementary methods:**
 - Kolmogorov-Smirnov test.
 - Visual inspection using Q-Q plots.
 - Histograms with normal curve superimposed.
- **Pre-established criteria:** $p > 0.05$ to accept normality according to protocol.
- **Planned action if violated:** Logarithmic transformation or use of non-parametric methods according to protocol specifications.

Sphericity Case:

- **Method:** Mauchly test for covariance matrix sphericity.
- **Pre-established criteria:** $p > 0.05$ to accept sphericity according to protocol.
- **Planned fixes if violated:**

- Greenhouse-Geisser (epsilon < 0.75).
- Huynh-Feldt (epsilon > 0.75).
- Lower limit (very small epsilon).

Homoscedasticity Case:

- **Method:** Levene test for equality of variances.
- **Application:** A residual differences between pairs of measurements.
- **Pre-established criteria:** $p > 0.05$ to accept homoscedasticity according to protocol.

4.3.2 For non-parametric tests (GAS):

- **Independence:** Verification of the intrasubject design.
- **Ordinal scale:** Confirmation of the ordinal nature of GAS scores.

4.4 Handling Missing Data

4.4.1 Planned Primary Analysis (Completed):

- Inclusion only of participants with complete data at the three planned time points.
- Systematic description of excluded participants and reasons according to protocol.

4.4.2 Pre-established Sensitivity Analysis:

- **Planned Method 1:** Last Observed Carried Out (LOCF).
- **Scheduled Method 2:** Worst-case scenario analysis (no change assignment).
- **Protocolized comparison:** Evaluation of agreement between methods according to a pre-established plan.

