2.2 Population Analysis

Target population: n = 24 estimated participants who meet inclusion criteria and complete evaluations in the three planned time points.

Pre-established criteria for inclusion in analysis:

- Participants aged 3-7 years with a confirmed diagnosis of ASD and/or associated DND according to DSM-V
- Signed informed consent
- Completion of the 14-week intervention protocol
- Complete data in the three temporary evaluations

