7. ADDITIONAL SENSITIVITY ANALYSIS

7.1 Analysis by Planned Exploratory Subgroups

- **Age:** Programmed comparison between group 3-5 years vs. 6-7 years.
- **Diagnosis:** Pre-established ASD vs. other DNDs.
- **Adherence:** Planned comparison $\geq 80\%$ vs. $< 80\%$ of completed sessions.

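### The primary analysis keeps only children who complete treatment and all assessments, and the planned worst case stops at no change, so dropout linked to poor progress is only partly tested

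*Combined protocol and SAP*

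**What the plan says.** SAP 2.2 lists criteria for entering the analysis. Two of them can be known only after treatment has started: "Completion of the 14-week intervention protocol" and "Complete data in the three temporary evaluations". The planned size is counted in the same way: "n = 24 estimated participants who meet inclusion criteria and complete evaluations in the three planned time points". No enrolment target and no dropout allowance are given.

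SAP 4.4.1 repeats the rule for the primary analysis ("Inclusion only of participants with complete data at the three planned time points") and adds a safeguard: "Systematic description of excluded participants and reasons according to protocol".

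SAP 4.4.2 plans two sensitivity analyses and a comparison of their agreement. Method 1 is given as "Last Observed Carried Out (LOCF", and Method 2 as "Worst-case scenario analysis (no change assignment".

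The stated target is wider than the analysis set. SAP 1.1 sets the primary objective for participants who received the intervention, and protocol 5.1 samples every eligible child in the study period.

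**The concern.** Selecting children on what happens after baseline changes the question. The mean change describes those who stayed, while the objective refers to those treated. In a controlled trial some of this selection may be common to both arms; here there is no second arm, so any selection passes straight into the headline change. A child treated for ten weeks, or assessed at weeks 0 and 15 but not 17, received the Model and yet does not count in the primary result.

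The planned sensitivity analyses leave three gaps.

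- No change is not the worst case. The primary outcome is a standard score and can fall. SAP 5.2.2 itself names a setback category for GAS, but nothing below baseline is tried for the Vineland-3 composite.
- For a child with only a baseline score, LOCF and no change give the same value, so agreement between them there carries no information. For a child missing only week 17, LOCF sets week 17 equal to week 15. That assumes the maintenance which SAP 1.2, item 4, sets out to examine.
- SAP 2.2 does not say whether its completion criteria are lifted for SAP 4.4.2. If they are not, nobody is left to impute.

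At stake is whether the reported change can be read as the change in treated children. Protocol 1.1 intends the results to inform parents, public agencies and insurers.

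**Working it through.** **The plan's own figures.** The Bonferroni level in SAP 4.5.2 reproduces: 0.05 / 3 = 0.0167. The size of 24 cannot be checked, because no effect, SD of change, power or dropout stands behind it. If 24 is the number of completers, enrolment would be 24/0.9 = 26.7 (27), 24/0.8 = 30 or 24/0.7 = 34.3 (35) at 10%, 20% or 30% dropout.

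**Inputs.** From the SAP: 24 completers (2.2), the 0.0167 level (4.5.2) and the bands in 5.2.1 (moderate 7.5–14.9 points, minimum 3–7.4). Assumed, because the documents give none: completer gain m = 7.5, proportion excluded d = 10%, 20% or 30%, mean change x in the excluded, and SD of change 10 (range 8 to 15). No change is read as no change from baseline.

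**Bias in the mean.** The all-enrolled mean is (1 − d)m + d·x. The completer bias is m minus this, which is d(m − x). The no-change estimate is (1 − d)m, with bias −d·x.

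| d | No-change estimate | True mean if x = 7.5 | x = 0 | x = −3 | x = −7.5 |
|---|---|---|---|---|---|
| 10% | 6.75 | 7.50 | 6.75 | 6.45 | 6.00 |
| 20% | 6.00 | 7.50 | 6.00 | 5.40 | 4.50 |
| 30% | 5.25 | 7.50 | 5.25 | 4.35 | 3.00 |

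At d = 20% the completer bias is 0, +1.50, +2.10 and +3.00 across the four values of x. The no-change bias is −1.50, 0, +0.60 and +1.50. So Method 2 is cautious when leavers gain, exact when they do not change, and too favourable when they decline.

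**Effect on the p-value.** Take the paired comparison of week 0 with week 17 and add k excluded children, each given a change v, to the 24 completers. With n = 24 + k:

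- mean = (24m + k·v) / n
- SS = 23·SD² + 24m² + k·v² − n·mean²
- t = mean / √(SS / ((n − 1)n)), on n − 1 degrees of freedom

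Example with m = 7.5, SD = 10, k = 6, v = 0: mean = 180/30 = 6.0; SS = 2300 + 1350 − 1080 = 2570; s = √(2570/29) = 9.41; t = 6.0/(9.41/√30) = 3.49; p = 0.0016. Completers alone give p = 0.0013. The zeros shrink the mean and its standard error together.

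A completer result exactly at the threshold has t = 2.581 on 23 degrees of freedom, so m = 2.581 × 10/√24 = 5.27. The table gives p for k = 3, 6 and 10 (11%, 20% and 29% of the total), with SD 10.

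| Change given to the excluded | From p = 0.0167 (m = 5.27) | From p = 0.0013 (m = 7.5) |
|---|---|---|
| 0 | 0.0171, 0.0175, 0.0178 | 0.0014, 0.0016, 0.0017 |
| −3 | 0.029, 0.046, 0.081 | 0.003, 0.006, 0.012 |
| −7.5 | 0.062, 0.160, 0.39 | 0.008, 0.030, 0.107 |

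From a threshold result, zeros give the same 0.0171 to 0.0178 at an SD of 8 or 15. A loss of 7.5 gives 0.083 to 0.61 at SD 8 and 0.041 to 0.18 at SD 15.

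**The case against.** The strongest reply is that the SAP already has a partial check. In the scenario where the excluded do not change, Method 2 returns the correct means of 6.75, 6.00 and 5.25. A reader might infer that the sensitivity analyses cannot reveal any bias; for the point estimate that is wrong. What stands is narrower: declines below baseline are untested, and the p-value hardly responds.

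A reader might also take upward bias as established. The documents do not support that. They give no dropout rate and no reasons, and the bias is zero if leavers gain as much as completers and downward if they gain more. The plan also describes the excluded and their reasons, evaluates missing data as Step 1 of SAP 5.1, and concedes in SAP 10.1 that the lack of a control group limits causal inference. These help, but they do not adjust the estimate, and SAP 10.1 does not mention attrition.

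Three further inferences do not hold.

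- A child missing only week 17 is not lost altogether: LOCF keeps the child, provided SAP 2.2 does not govern the sensitivity analyses.
- The adherence comparison in SAP 7.1, at 80% "of completed sessions", need not have an empty lower group. Completion of the protocol is not defined by a percentage of sessions. The comparison does omit children who stopped.
- The fall from the moderate to the minimum band comes from starting at its 7.5-point edge. With completers gaining 12 and the excluded 0, the means are 10.8, 9.6 and 8.4, all still moderate.

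Finally, a mixed model assumes data missing at random. For children with only a baseline like that of the completers, it implies about the completers' change, so it does not by itself correct for dropout due to poor progress. This stands, and it shapes the fix.

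**Conclusion.** The point holds as a risk that the plan tests only in part. The primary set is conditioned on treatment completion and full data, which is narrower than the stated objective. The possible upward bias is d(m − x). With a completer gain of 7.5 and 10% to 30% excluded, it runs from 0 if the excluded gain equally, through 0.75 to 2.25 points if they do not change, to 1.5 to 4.5 points if they lose 7.5. Method 2 then leaves 0.75 to 2.25 points of that last range uncovered. On significance, a threshold result moves only to 0.0171–0.0178 under no change, against 0.029–0.081 if the excluded lose 3 points and 0.062–0.39 if they lose 7.5 (SD of change 10). A stronger completer result (p = 0.0013) withstands a loss of 3 points but not always one of 7.5.

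All gains, SDs and dropout shares here are assumptions. If few children leave, or if leaving is unrelated to progress, the result will barely change. Because the size is unknown and a partial check exists, this is a should-fix.

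**What to change.** 1. In SAP 2.2 and 4.4.1, define the primary set as all enrolled children with a baseline Vineland-3, whatever number of sessions they completed. Fit a linear mixed model for weeks 0, 15 and 17 with unstructured covariance to all available scores, and state that it is valid under missing at random. Keep the completer analysis as supportive.
2. State in SAP 2.2 that the completion criteria do not apply to the sensitivity analyses.
3. In SAP 4.4.2, rename Method 2 as baseline carried forward. Replace LOCF with a tipping-point analysis that gives missing children changes of 0, −3, −7.5 and −15 points and reports where the conclusion changes, both for the week 0 to week 17 comparison and for the SAP 5.2.1 band. This analysis, and not the mixed model, addresses dropout for poor progress.

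The cost is SAP wording and SPSS MIXED syntax, using scores already collected. The downsides are slightly more analysis work and possibly a less favourable estimate.

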4.5 Significance Criteria and Adjustments for Multiple Comparisons

4.5.1 Level of Significance:

- **Primary analysis:** $\alpha = 0.05$ (bilateral).
- **Confidence intervals:** 95%.

4.5.2 Adjustments for Multiple Comparisons:

- **Within each variable:** Bonferroni correction for post-hoc comparisons.
- **Among secondary variables:** No adjustment (exploratory analysis).
- **Number of comparisons by ANOVA:** 3 post-hoc comparisons.

Bonferroni adjustment formula: $\alpha_{\text{ajustado}} = \alpha / \text{number of comparisons} = 0.05 / 3 = 0.0167$.

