4.2 Inferential Analysis

4.2.1 Primary Variable Analysis

Main method: One-factor (time) repeated measures ANOVA with three levels.

- **Intrasubject factor:** Time (3 levels: week 0, 15, 17).
- **Dependent variable:** ABC Vineland-3 score.
- **Null hypothesis:** $H_0: \mu_0 = \mu_{15} = \mu_{17}$ (there are no differences between moments).
- **Alternative hypothesis:** H_1 : At least one mean differs.

Post-hoc comparisons: Bonferroni's method for multiple comparisons:

- Week 0 vs. Week 15.
- Week 0 vs. Week 17.
- Week 15 vs. Week 17.

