4.2.2 Analysis of Secondary Variables

Quantitative variables (Vineland-3 Domains, FOS):

- Repeated measures ANOVA (procedure identical to primary variable).
- Bonferroni correction for multiple comparisons.
- Analysis of planned contrasts (linear and quadratic).

Ordinal variables (GAS):

- Friedman's test for repeated measures ($k = 3$ moments).
- Dunn's post-hoc comparisons with Bonferroni's correction.
- Analysis by individual objective (Objective 1, 2, and 3).

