5. SPECIFIC ANALYSIS PROCEDURES

5.1 Planned Sequence of Analysis

Step 1: Planned descriptive analysis of baseline characteristics and systematic evaluation of missing data.

Step 2: Protocolized verification of statistical assumptions for each variable according to prespecified methods.

Step 3: Planned analysis of primary variable (ABC Vineland-3):

- Repeated measures ANOVA according to protocol specifications.
- Post-hoc comparisons conditioned to significant F.
- Preset calculation of effect sizes.

Step 4: Scheduled analysis of quantitative secondary variables (Vineland-3 domains, FOS):

- Repeated measures ANOVA for each variable according to protocol.
- Post-hoc comparisons with prespecified Bonferroni correction.

Step 5: Planned ordinal secondary variable (GAS) analysis:

- Friedman's test for each objective according to design.
- Dunn's post-hoc comparisons according to protocol.

Step 6: Preset sensitivity analysis for missing data based on specified methods.

Step 7: Planned synthesis of findings and interpretation according to pre-established criteria.

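### Single-step Bonferroni on the three Vineland-3 pairs is valid, but a step-down rule holds the same 5% family error and never detects less

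*Combined protocol and SAP*

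**What the plan says.** SAP 4.2.1 analyses the Vineland-3 composite by repeated measures ANOVA over weeks 0, 15 and 17. It then compares 0 with 15, 0 with 17 and 15 with 17 by "Bonferroni's method for multiple comparisons". SAP 4.2.2 gives the Vineland-3 domains the same procedure, with "Bonferroni correction for multiple comparisons". Within each variable, SAP 4.5.2 requires "Bonferroni correction for post-hoc comparisons"; it counts "3 post-hoc comparisons" per ANOVA and divides 0.05 by three, so each pair is tested at 0.0167. For the primary variable, SAP 5.1 Step 3 adds a gate: "Post-hoc comparisons conditioned to significant F".

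Two of the pairs carry stated aims. Week 17 minus week 0 is the primary variable (SAP 3.1). Week 15 against week 17 is the maintenance objective (SAP 1.2). SAP 2.2 expects "n = 24 estimated participants", all with complete data. Neither document contains a step-down rule, a fixed testing order, a planning effect or a power calculation.

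**The concern.** Three means give three equalities, and these are logically linked: if one is false, at most one of the other two can be true. Once one pair has been declared different at 0.0167, dividing alpha by three for the remaining pairs guards against a combination of errors that can no longer occur. Single-step Bonferroni ignores this.

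At stake is power in a sample of about 24, on the contrast that defines the primary variable and on the one that addresses maintenance. A real week 0 to 17 change, or a real loss after the intervention stops, would be missed more often than the plan's own error limit requires. The point applies to the composite and the three domains. FOS is left out because protocol 9.1 schedules it only at weeks 0 and 15, which gives one pair.

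**Working it through.** **The plan's figure.** 0.05 / 3 = 0.01667, which rounds to 0.0167. It reproduces.

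**The rules compared**, applied to the three unadjusted paired p-values in ascending order:
- Bonferroni: 0.0167 for each.
- Holm: 0.0167, 0.025, 0.05, stopping at the first failure.
- Shaffer: smallest at 0.0167; if rejected, the other two at 0.05 each.

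Each threshold is at least as large as the one in the rule above it, so Holm rejects all that Bonferroni rejects, and Shaffer all that Holm rejects. The F gate can only remove rejections, so it cannot raise the family error.

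**Inputs.** From the SAP: n = 24 (2.2) and two-sided alpha 0.05 (4.5.1). Assumed: SD 15, which is the normative SD in SAP 3.1; correlations of 0.64 or 0.80 with week 0 and 0.92 between weeks 15 and 17, taken from the test-retest range 0.64-0.92 in protocol 8.1; and the true mean changes.

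**Analytic check of the Bonferroni base.** SD of a difference = 15 × √(2(1 − r)); noncentrality = change / (SD of difference / √24). The critical t on 23 df is 2.58 at 0.0167, 2.40 at 0.025 and 2.07 at 0.05.
- 5 points, r = 0.64: SD 15 × √0.72 = 12.73; noncentrality 5 / 2.598 = 1.92; power at 0.0167 is 28%.
- 5 points, r = 0.80: SD 15 × √0.40 = 9.49; noncentrality 5 / 1.937 = 2.58; power 51%.
- 3 points, r = 0.92: SD 15 × √0.16 = 6.00; noncentrality 3 / 1.225 = 2.45; power 46% before the gate.

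**Simulation** (40,000 trials per scenario, paired t-tests, Greenhouse-Geisser F gate applied). True changes are +8 at week 15 and +5 at week 17:

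| Pair | r with week 0 | Bonferroni | Holm | Shaffer |
|---|---|---|---|---|
| 0 vs 17 | 0.64 | 28% | 40% | 45% |
| 0 vs 17 | 0.80 | 51% | 64% | 69% |
| 15 vs 17 | 0.64 | 38% | 47% | 51% |
| 15 vs 17 | 0.80 | 45% | 59% | 63% |

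For week 0 vs 17 the gains are 40 − 28 = 12 and 64 − 51 = 13 points with Holm, and 45 − 28 = 17 and 69 − 51 = 18 with Shaffer. For 15 vs 17 they are 9 and 14 points with Holm, and 13 and 18 with Shaffer.

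**Other patterns.** For week 0 vs 17, +8/+8 and +5/+8 give gains of only about 1 to 6 points; for example +8/+8 at r = 0.64 goes from 69% to 72% (Holm) or 75% (Shaffer). With +5/+5 at r = 0.64 it goes from 28% to 30% or 33%. For week 15 vs 17, lowering that pair's correlation to 0.80 (r = 0.80 with week 0) gives 17% rising to 26% or 31%.

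**Error rates.** With all means equal and no gate, the family error is about 4% and the same under all three rules, because each needs a first rejection at 0.0167. With weeks 15 and 17 equal and week 0 different (+8/+8 or +15/+15), false rejection of that one true equality is about 1.6% under Bonferroni and about 4-5% under step-down.

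**The case against.** The strongest reply is that nothing here is wrong. Bonferroni is valid, prespecified and correctly computed, the protocol's main objective is descriptive, and the secondary results are declared exploratory. That stands, and it fixes the weight of the point.

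A reader might infer that the current rule gives up power and gets nothing back. The error rates do not support that. When skills really are maintained, Bonferroni raises a false alarm on week 15 vs 17 about 1.6% of the time, against 4-5% under step-down. That is extra protection, though beyond the 5% family limit the plan sets itself.

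A reader might also take 17 to 18 points as the general gain for the primary contrast. That figure belongs to Shaffer alone and to a partial loss by week 17 (+8/+5), where week 0 vs 17 is not the largest contrast and so benefits most from the later steps. The documents name no expected pattern, so they do not support a single figure.

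A further objection is that, since week 17 minus week 0 is the defined primary variable, testing it first at the full 0.05 would serve it better: 84% at +8/+8 with r = 0.64, against 75-78% for Shaffer across week 15-17 correlations of 0.92 to 0.64. This is a fair alternative. It does not rescue the current rule, which Holm and Shaffer dominate in power at the same family error limit.

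Finally, more power on week 15 vs 17 helps to detect a loss, but a non-significant result does not show maintenance under any of these rules.

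**Conclusion.** The point holds as a cheap improvement. The 0.0167 threshold is correct and no conclusion drawn under it would be invalid. A step-down rule keeps the 5% family error and never detects less.

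Under the stated assumptions and with the gate applied, the gain for week 0 vs 17 runs from about 1 to 6 points when week 17 is level with or above week 15 (+8/+8, +5/+8) to 12-13 (Holm) or 17-18 (Shaffer) when part of the gain is lost (+8/+5). For a 3-point week 15 vs 17 difference it is 9-14 (Holm) or 13-18 (Shaffer) points, and less if that pair correlates below 0.92. That the gain is never negative follows from the ordering of the thresholds. Its size rests on assumed SD, correlations and true changes that the documents do not supply.

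**What to change.** In SAP 4.5.2, replace the common 0.0167 for Vineland-3 variables with one named step-down rule, chosen before the data are analysed. Order the three unadjusted paired p-values, then use either Holm (0.0167, 0.025, 0.05, stopping at the first failure) or Shaffer (smallest at 0.0167; if rejected, 0.05 for each of the other two). Refer to it from 4.2.1 and 4.2.2, keep the F gate in 5.1, and report step-down adjusted p-values. State also that a non-significant week 15 vs 17 result will not be read as evidence of maintenance. If the team would rather protect the primary contrast directly, prespecifying week 0 vs 17 as the first test at 0.05 is the alternative to consider.

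The cost is SAP wording and the ordering of three p-values per variable; no new data are needed. SAP 8.2 treats a change in primary analysis methods as a major deviation, requiring the principal investigator's approval and a protocol amendment. Two downsides should be accepted openly: adjusted p-values will no longer correspond to one common interval width, and false rejection of a true week 15 = week 17 rises from about 1.6% to 4-5%, within the family 5%.

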4.6 Calculation of Effect Sizes

4.6.1 For Repeated Measures ANOVA:

- **Partial eta square (η^2):** To assess magnitude of effect
 - Small: $\eta^2 = 0.01$
 - Median: $\eta^2 = 0.06$
 - Large: $\eta^2 = 0.14$

4.6.2 For post-hoc comparisons:

- **Cohen's d:** For differences between pairs of means
 - Small: $d = 0.20$
 - Median: $d = 0.50$
 - Large: $d = 0.80$

Formula: $d = (\mu_1 - \mu_2) / \text{spooled}$

4.6.3 For non-parametric tests:

- **r effect:** $r = Z/\sqrt{N}$ for Friedman test
 - Small: $r = 0.10$
 - Median: $r = 0.30$
 - Large: $r = 0.50$

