3.2.2 Goal Attainment Scaling (GAS)

- **Objectives 1, 2 and 3:** Individually defined by family and therapists.
- **Scale:** 5-point ordinal (-2 to +2).
- **Conversion:** T-scores using the Kiresuk-Sherman formula (mean = 50, SD = 10).

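### SAP 4.6.3 assigns r = Z/√N to the Friedman test, which yields no Z, and leaves N undefined, so the GAS effect-size label depends on an improvised conversion

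*Combined protocol and SAP*

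**What the plan says.** SAP 4.2.2 analyses the GAS scores with "Friedman's test for repeated measures" at k = 3 time points, followed by "Dunn's post-hoc comparisons with Bonferroni's correction". SAP 5.1, Step 5, makes the unit of analysis the individual goal: "Friedman's test for each objective according to design".

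SAP 4.6.3 covers effect sizes for non-parametric tests in one line. It gives r = Z/√N and labels it "for Friedman test". The benchmarks below it are 0.10 (small), 0.30 (median) and 0.50 (large).

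The sample size is in SAP 2.2: "n = 24 estimated participants who meet inclusion criteria and complete evaluations in the three planned time points". That is 24 children, or 24 × 3 = 72 observations per objective. SAP 4.6.3 does not say which of these N stands for, or where Z comes from. No other section supplies a Z, an N or a different omnibus effect size for GAS.

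**The concern.** The formula r = Z/√N presupposes a test statistic that is approximately standard normal, such as one from a two-group or paired comparison. A Friedman test over three time points has k − 1 = 2 degrees of freedom. Its statistic is a chi-square, which has no sign and is not the square of a single Z. There is nothing to put in the numerator.

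An analyst following the SAP would have to invent a conversion and choose N, probably after seeing the results. The small, median or large label for each of the three GAS objectives would then partly reflect those choices. SAP 4.6.3 exists to fix that label in advance, and as written it does not.

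**Working it through.** The SAP states a formula and benchmarks but no numerical value of r, so there is no figure of its own to reproduce. The check is how far the label moves under the conversions an analyst might use.

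**Inputs**
- Children: 24 (SAP 2.2). Time points: k = 3 (SAP 4.2.2). Observations per objective: 24 × 3 = 72; per pair of time points: 24 × 2 = 48.
- Benchmarks for r: 0.10, 0.30, 0.50 (SAP 4.6.3), read here as lower cut-points for each label. The SAP does not say so, which makes this an assumption.
- Illustrative chi-square values: 6.0, 20, 30, and the maximum N(k − 1) = 24 × 2 = 48.

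**Conversions tried**
- p-to-Z: Z is the normal quantile matching the two-sided Friedman p-value on 2 df.
- Root: Z = √(chi-square).
- Comparator: Kendall's W = chi-square/[N(k − 1)] = chi-square/48.

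**Results**

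| Chi-square | Z (p-to-Z) | r, N = 24 | r, N = 72 | r by root, N = 24 | r by root, N = 72 | W |
|---|---|---|---|---|---|---|
| 6.0 (p = 0.050) | 1.96 | 0.40 | 0.23 | 0.50 | 0.29 | 0.125 |
| 20 | 4.08 | 0.83 | 0.48 | 0.91 | 0.53 | 0.42 |
| 30 | 5.12 | 1.05 | 0.60 | 1.12 | 0.65 | 0.63 |
| 48 | 6.61 | 1.35 | 0.78 | 1.41 | 0.82 | 1.00 |

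The first row in full: 1.96/√24 = 1.96/4.90 = 0.40; 1.96/√72 = 1.96/8.49 = 0.23; √6/√24 = √0.25 = 0.50; W = 6/48 = 0.125.

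**Effect on the label.** At chi-square 6.0 the same data are median, small or large depending on the route and N. At chi-square 20 the p-to-Z route gives large with N = 24 and median with N = 72. Changing N from 24 to 72 divides r by √(72/24) = 1.73 whatever the data. By the root route with N = 24, the 5% critical value of 5.99 already gives √(5.99/24) = 0.50, so essentially every significant result would be called large. Under no effect, 20,000 simulated datasets without ties gave a mean r of 0.26 by that route, and 36% reached 0.30 or more.

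**When r exceeds 1.** With N = 24, the root route passes 1 when chi-square is above 24 (W above 0.5). The p-to-Z route passes 1 when Z is above √24 = 4.90, which is chi-square above 27.7 (W above 0.58). With N = 72 the maxima are 0.78 and 0.82. With N = 48 they are 6.61/√48 = 0.95 and √(48/48) = 1.00.

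**Dunn comparisons.** These do give a Z: the difference in mean ranks divided by √[k(k + 1)/(6N)], without tie correction. The largest possible difference is 3 − 1 = 2, so the maximum Z is 2/√(12/144) = 6.93. Dividing by √24 gives 1.41; dividing by √48 gives 1.00.

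**The case against.** The strongest counter-argument is that the heading of SAP 4.6.3 covers non-parametric tests in general. The planned Dunn comparisons produce a Z, so r may simply have been meant for them and mislabelled. That is plausible, but the text names the Friedman test, and even on this reading N still has to be defined: with N = 24 pairs, Dunn's Z can give r of 1.41.

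A reader might infer that the formula produces impossible values as a matter of course. The documents do not support that. The SAP contains no conversion to Z, and r above 1 appears only once an analyst supplies one and also takes N as 24. The supportable statement is that Z and N are unspecified.

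A reader might also infer that the interpretation of GAS rests on r. It does not. SAP 5.2.2 sets clinical interpretation through T-score bands, SAP 4.1.2 provides frequencies, medians and confidence intervals for proportions, and SAP 4.5.2 and 10.3 treat secondary outcomes as exploratory. Nor can the problem be carried over to the primary Adaptive Behavior Composite analysis: SAP 4.3.1 allows non-parametric methods if normality fails, but it does not name Friedman as the fallback.

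One further reservation stands. Protocol 8.2 sets the baseline GAS level at −2, the floor of the scale, so scores can only stay or rise. That pushes any omnibus effect size upward, including W. Kendall's W removes the undefined step but not this feature of the scale.

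**Conclusion.** The rule is wrong as written. A three-time-point Friedman test gives a chi-square on 2 df and no Z, and N is undefined, so the prespecified effect size for GAS cannot be computed without an added step. The possible additions are not equivalent: a borderline-significant result can be labelled small, median or large. These figures assume 24 complete cases and the benchmarks used as lower cut-points.

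The reach is narrow. What is affected is a descriptive label on an exploratory secondary outcome. No p-value, primary result or T-score band changes. The SAP should still be corrected, because the error is clear and almost free to remove.

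**What to change.** In SAP 4.6.3, replace the Friedman line with Kendall's W = chi-square/[N(k − 1)], where N is the number of children analysed for that objective (chi-square/48 for N = 24 and k = 3). W lies between 0 and 1 and follows directly from the planned statistic. Remove the 0.10/0.30/0.50 benchmarks from that line; they belong to r. If a verbal label for W is wanted, its cut-points should be stated before analysis.

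If r is kept, attach it to the Dunn pairwise comparisons already planned in SAP 4.2.2 and 5.1, and define N as the observations per pair (48 for 24 children). It then cannot exceed 1; that bound is computed without tie correction. Attaching r to signed-rank tests would not match the plan, which contains none.

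The cost is one or two lines of SAP text, with no new data or tests. The downside for the authors is that the effect-size labels may look less favourable than under some readings of the present formula.
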